### 9.4 STATISTICAL ANALYSES

#### 9.4.1 GENERAL APPROACH

For descriptive statistics, continuous variables will be presented using means with standard deviation. Categorical variables will be presented using percentages with 95% confidence intervals. All tests will be two sided at 5% significance level. Normality will be assessed, and nonparametric tests used where appropriate.

We will prespecify several covariates for regression models with special attention to emerging constructs in the pain literature, specifically FM survey score and PainDETECT, that may be associated with treatment response. However, we will also perform exploratory analyses given our focus on hypothesis generation.

#### 9.4.2 ANALYSIS OF THE PRIMARY ENDPOINT(S)

The primary outcome (PROMIS Pain Interference) is a continuous measure and utilizes a standardized, publicly available scoring system. We will report mean and standard deviation for each group.

Given pilot RCT design, we will use a simple posttreatment comparison of pain interference at 3-months. We will compare means with t-test. All tests will be two-sided at 5% significance level. Of note, data collected at 6-month interval will be analyzed as an exploratory outcome.

We will estimate effect size by calculating Hedges'  $g$  (rather than Cohen's  $d$  because groups are different sizes) for pain interference at 3-months, which we will use in planning for future efficacy trial.

As part of our exploratory analyses, we plan to categorize patients as "responders" vs "non-responders." "Responder" will be defined as an improvement of at least 2.5 on PROMIS Pain Interference from baseline to 3-months. We will compare differences in contributing pain conditions, pain characteristics such as Fibromyalgia Survey Score or PainDETECT, and comorbid mental health factors that may be associated responder status. We tentatively plan to use logistic regression to compare factors associated with responder status. We will use these exploratory analyses to inform structure of our future efficacy trial.

We will be using an intent to treat analysis. Patients may elect to skip questions on the questionnaire and therefore it is possible that we encounter some missing data or incomplete questionnaires. We will report the proportion of missing outcome per group and characteristics of patients with missing data. If we encounter more than 5% missing data, we plan to conduct sensitivity analyses to assess effect of missingness on results.

---

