## 1 PROTOCOL SUMMARY

### 1.1 SYNOPSIS

Title:	Novel web-based, self-directed intervention for chronic pelvic pain
Grant Number:	1K23HD09928301A1
Study Description:	We propose to conduct a pilot randomized controlled trial to evaluate preliminary effectiveness of a web-based, self-management program for patients with CPP and phenotypic factors that predict positive response. Our overall hypothesis is patients with CPP who have access to this novel intervention will demonstrate improved in pain, physical function, and quality of life.
Objectives*:	
Primary Objective:
 

- To evaluate effectiveness of the intervention by comparing pain interference among intervention group versus control group following the intervention.

 
Secondary Objectives:
 

- To compare pain intensity among intervention group versus control group.

- To compare physical function and health-related self-efficacy among intervention group versus control group.

Endpoints*:	
Primary Endpoint:
 

- PROMIS Pain Interference SF 4a at 3 months.

 
Secondary Endpoints:
 

- PROMIS pain intensity from baseline to 3 months.

- PROMIS Self Efficacy for Managing Symptoms SF 4a at 3 months

Study Population:	We will recruit 69 women (female sex assigned at birth) with chronic pelvic pain.
Phase* or Stage:	Stage 1 on NIH Stage Model for behavioral interventions
Description of Sites/Facilities Enrolling Participants:	Department of Obstetrics and Gynecology and the Chronic Pain and Fatigue Research Center (CPFRC) at the University of Michigan. Patients will be recruited from the Chronic Pelvic Pain and Endometriosis referral clinic at Michigan Medicine, where our group of specialty-trained gynecologists see approximately 150 patients with CPP every month.

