### 6.4 STUDY INTERVENTION/EXPERIMENTAL MANIPULATION ADHERENCE

Each month, we will ask intervention group participants to indicate which skills they have utilized in the past month. However, we are unable to track website utilization for individual patients based on the current website design.

Relative to questionnaires, we will require completion of baseline questionnaires in order to participate in the study. We will not dismiss patients from participating if they do not complete questionnaires but will send multiple reminders and monetary incentives for participating.

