## 9 STATISTICAL CONSIDERATIONS

### 9.1 STATISTICAL HYPOTHESES

- Primary Endpoint:

We hypothesize that patients who receive the *My Pelvic Plan* intervention in addition to usual care will demonstrate improvement on PROMIS Pain Interference SF 4a from baseline to 3-month follow-up. Alternatively, our null hypothesis is that there will be no difference in Pain Interference from baseline to 3-month follow up. As this is a pilot study, we will be evaluating preliminary program effectiveness by comparing the intervention group to an active control group and will use this information to generate effect size for a trial to evaluate efficacy.

- Secondary Endpoints:

We hypothesize that patients who receive the *My Pelvic Plan* intervention in addition to usual care + symptom tracker will demonstrate improvements on PROMIS Pain Intensity and PROMIS Self Efficacy for Managing Symptoms SF 4a from baseline to 3-month follow-up. Alternatively, our null hypothesis is that there will be no difference in Pain Intensity and Self-Efficacy from baseline to 3-month follow up.

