#### 9.4.3 ANALYSIS OF THE SECONDARY ENDPOINT(S)

Secondary outcomes (PROMIS Pain Intensity and PROMIS Self-Efficacy) are also continuous measures and utilize a standardized, publicly available scoring system. We will use a simple posttreatment comparison of pain interference at 3-months. All tests will be two-sided at 5% significance level. Of note, data collected at 6-month interval will be analyzed as an exploratory outcome.

We will be using an intent to treat analysis. Patients may elect to skip questions on the questionnaire and therefore it is possible that we encounter some missing data or incomplete questionnaires. We will report the proportion of missing outcome per group and characteristics of patients with missing data. If we encounter more than 5% missing data, we plan to conduct sensitivity analyses to assess effect of missingness on results.

---

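### The primary 3-month t-test leaves out a baseline score the trial already collects, costing precision in the effect size the pilot is meant to supply; Sections 9.1 and 9.4.3 need matching repairs

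*Combined protocol and SAP*

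**What the plan says.** - **Primary analysis (9.4.2).** "Given pilot RCT design, we will use a simple posttreatment comparison of pain interference at 3-months. We will compare means with t-test". The reason given is the pilot design. Hedges' g is taken for the same 3-month outcome and is to be used in planning an efficacy trial.
- **Endpoint (1.1).** "PROMIS Pain Interference SF 4a at 3 months", which agrees with that test.
- **Baseline (6.4).** "we will require completion of baseline questionnaires in order to participate in the study". At 3 months, baseline pain interference is used only to define exploratory responders (9.4.2, 9.4.9). Section 9.4.1 promises covariates for regression models. It singles out the fibromyalgia survey score and painDETECT, not baseline pain interference, and does not tie them to the primary comparison.
- **Hypotheses (9.1).** The intervention group "will demonstrate improvement on PROMIS Pain Interference SF 4a from baseline to 3-month follow-up", and "our null hypothesis is that there will be no difference in Pain Interference from baseline to 3-month follow up". The same paragraph also speaks of "evaluating preliminary program effectiveness by comparing the intervention group to an active control group".
- **Secondary analysis (9.4.3).** Having named pain intensity and self-efficacy as the secondary outcomes, it continues: "We will use a simple posttreatment comparison of pain interference at 3-months". The synopsis lists one of these endpoints as "PROMIS pain intensity from baseline to 3 months".
- **Purpose (9.2).** The 69 patients are to show feasibility and yield effect size estimates. Power for pain interference is expressly not sought.

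**The concern.** A baseline measurement of the outcome usually explains part of the variation in the follow-up measurement. Leaving it out makes the estimated arm difference noisier than it needs to be. Power is not the issue, since the plan disclaims it. The issue is that an effect size estimate is one of the two products named in Section 9.2, and its precision can be improved with data already in hand. Section 9.4.5 plans baseline comparisons between arms but says nothing about what to do if they differ.

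The wording faults are separate and do not depend on any correlation. The null in Section 9.1 describes change over time without naming a contrast between arms, while the planned test is a contrast between arms. Read literally, Section 9.4.3 specifies no comparison of pain intensity or self-efficacy.

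**Working it through.** **Inputs.** N = 69 (9.2) and 2:1 allocation (6.3) give 69 × 2/3 = 46 and 69 × 1/3 = 23. The split is nominal, because blocks of 4 cannot hold an exact 2:1 ratio. Tests are two-sided at 5% (9.4.2). Full retention is assumed. The documents state no SD, so results are in SD units. They state no r, so 0.3, 0.5 and 0.7 are assumed. The plan derives no figure for N or precision, so there is none to reproduce.

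**As planned.** SE = sqrt(1/46 + 1/23) = 0.255 SD. The half-width is t(0.975; 67 df) × SE = 0.51 SD. The full interval is 2 × 0.51 = 1.02 SD wide. The effect range that Section 4.2 cites for integrated interventions, 0.3 to 0.8, spans 0.5.

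**With ANCOVA on baseline.** The variance is multiplied by (1 − r²), and by (1 + 1/65) for estimating the slope. The half-width is t(0.975; 66 df) × 0.255 × sqrt(1 − r²) × sqrt(1 + 1/65). The last column, 69/(1 − r²), is the size of an unadjusted trial with the same precision, ignoring the slope cost.

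| assumed r | variance relative to t-test | half-width (SD) | 69/(1 − r²) |
|---|---|---|---|
| 0.3 | 0.92 | 0.49 | 76 |
| 0.5 | 0.76 | 0.44 | 92 |
| 0.7 | 0.52 | 0.37 | 135 |

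Setting (1 − r²)(1 + 1/65) = 1 gives r = 0.12. Above that value, adjustment gains precision.

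**Chance imbalance.** The probability of a baseline gap above 0.25 SD in either direction is 2 × [1 − Φ(0.25/0.255)], about 33%. With equal variances, a gap shifts the expected 3-month difference by r times the gap. For a gap of 0.25 SD that is 0.3 × 0.25 = 0.075, 0.5 × 0.25 = 0.125 or 0.7 × 0.25 = 0.175 SD.

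**Simulation check.** With 10,000 runs per r and a true difference of 0.5 SD, the 3-month t-test, the change-score comparison and ANCOVA all averaged about 0.50, so none is biased. The SDs of the estimates, in that order, were:
- r = 0.3: 0.253, 0.300, 0.243
- r = 0.5: 0.253, 0.256, 0.222
- r = 0.7: 0.254, 0.197, 0.182

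The change-score variance factor is 2(1 − r), which exceeds 1 below r = 0.5. Testing change scores to match the wording of Section 9.1 would therefore lose precision there.

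**Standardising g.** Dividing the adjusted difference by the ANCOVA residual SD would multiply g by 1/sqrt(1 − r²). That is 1/sqrt(0.64) = 1.25 at r = 0.6 and 1/sqrt(0.51) = 1.40 at r = 0.7.

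**The case against.** The strongest reply is that nothing invalid is planned. The t-test matches the 3-month endpoint, is unbiased under randomisation, and has a standard error that already allows for chance imbalance. The authors chose it openly for a pilot that disclaims power and is also about feasibility. All of this stands, and it makes the point a recommendation on efficiency.

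The reply is also right that the gain may be small. At r = 0.3 the half-width falls only from 0.51 to 0.49 SD, and no document says what r will be. An ANCOVA adopted without naming the SD for g could do harm: an inflated g carried forward unchanged would undersize the next trial.

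Two stronger readings are tempting, and the documents support neither.
- A reader might infer from the null in Section 9.1 that regression to the mean, in patients selected for pain, could produce a positive result. No within-group test is planned. The same paragraph and the objectives in Sections 1.1 and 3 describe a comparison between arms, in which regression to the mean is expected equally. The entry threshold in Section 5.1 is also a worst-pain rating, not pain interference.
- A reader might infer that a baseline imbalance carries over in full to the result. It carries over only by about r times the gap.

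The reply does not answer why a baseline score already collected should be left out. Pilot status is no reason when the estimate itself is a product of the pilot.

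**Conclusion.** The point holds as avoidable imprecision plus two wording faults. It should be changed before analysis, but it does not make the planned test wrong. The reduction in half-width runs from 0.02 SD (0.51 to 0.49) at r = 0.3 to 0.14 SD (0.51 to 0.37) at r = 0.7. These figures rest on the assumed r, the nominal 46:23 split, equal variances and full retention. The direction of the gain holds for any r above about 0.12.

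The fault in Section 9.4.3 is certain from the text. In Section 9.1 the between-arm intention is present and only the null statements miss it, so the aim does not change. It would go too far to conclude that the planned effect size is biased.

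**What to change.** - **9.4.2.** Make the primary analysis ANCOVA of the 3-month pain interference T-score on arm and baseline T-score. Report the adjusted difference with a 95% CI. Keep the raw means, SDs and t-test as supportive.
- **Hedges' g (9.4.2).** Define it as the adjusted difference divided by the unadjusted pooled SD, with a 95% CI, so that adjustment does not inflate it.
- **Missing baseline.** Section 9.4.2 lets patients skip questions, so a few baseline scores may be absent. Keep those participants by a simple prespecified method, such as mean imputation of the baseline covariate.
- **Baseline timing.** Sections 7.1 and 8.2 suggest that randomisation comes before the baseline questionnaire, with website access following it. Confirm that baseline is completed before allocation is revealed.
- **9.4.3.** Replace pain interference with pain intensity and self-efficacy, each analysed by the same model with its own baseline. This also settles the synopsis wording for pain intensity: with baseline as a covariate, modelling change or the 3-month score gives the same arm difference.
- **9.1.** State the primary and secondary nulls as zero between-arm difference at 3 months.

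The cost is wording in three sections and one check on procedure. No new data or patients are needed.

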#### 9.4.3 ANALYSIS OF THE SECONDARY ENDPOINT(S)

Secondary outcomes (PROMIS Pain Intensity and PROMIS Self-Efficacy) are also continuous measures and utilize a standardized, publicly available scoring system. We will use a simple posttreatment comparison of pain interference at 3-months. All tests will be two-sided at 5% significance level. Of note, data collected at 6-month interval will be analyzed as an exploratory outcome.

We will be using an intent to treat analysis. Patients may elect to skip questions on the questionnaire and therefore it is possible that we encounter some missing data or incomplete questionnaires. We will report the proportion of missing outcome per group and characteristics of patients with missing data. If we encounter more than 5% missing data, we plan to conduct sensitivity analyses to assess effect of missingness on results.

---

#### 9.4.4 SAFETY ANALYSES

N/A

---

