## 1.2 SCHEMA

### Flow Diagram

### 1.3 SCHEDULE OF ACTIVITIES

	Pre-consent	0 month Day 0 $\pm$ 14	1 month Day 30 $\pm$ 14	2 month Day 60 $\pm$ 14	3 month Day 90 $\pm$ 14	4 month Day 120 $\pm$ 14	5 month Day 150 $\pm$ 14	6 month Day 180 $\pm$ 14
Review eligibility	x	x						
Consent		x						
Randomization		x			x			
Adverse Event Reporting		x	x	x	x	x	x	x
Intervention								
Access My Pelvic Plan (Intervention group)		x	x	x	x	x	x	x
Access Monitoring Progress (Control group)		x	x	x	x	x	x	x
Outcome evaluation								
Questionnaire		x			x			x
Current treatment survey		x						x
Utilization survey (Intervention group)			x	x	x	x	x	x
Focus group (n=20, Intervention group)					x			

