### *Intervention group*

Patients in the intervention group will receive access to the *My Pelvic Plan* website (<https://www.mypelvicplan.com/>), which is a self-directed program which integrates patient education about conditions that frequently contribute to pelvic pain, as well as instruction on cognitive and behavioral restructuring, self-administration of acupuncture, engaging in physical activity, and a brief introduction to pelvic floor physical therapy techniques. They will have open access to the program over the 6-month intervention period. The intervention will be comprised of an active (12-week) phase and a maintenance (3-month) phase. During the active phase, we will use an established tailoring program to direct participants to particular modules or skills that are likely to be most relevant for their individual symptoms and characteristics. All intervention participants will receive a weekly text or email prompt directing them to a specific module. All participants will receive prompts to the same modules for the first four weeks of the study. During the next 8 weeks, participants will receive prompts to modules that corresponded to their most impactful symptoms on their baseline questionnaires. Following the 12-week active phase, all participants will enter the maintenance phase, during which they will receive monthly prompts to Monitoring Progress symptom tracker module.

Patients will have open access to the program over the 6-month intervention period. While they will receive text or email prompts to visit specific modules, they will ultimately choose how they navigate and utilize the program and we will not prescribe a specific schedule or utilization frequency.

We are unable to track website utilization for specific users. However, we will send an email link to a survey once per month which will ask which skills (from the *Managing Symptoms* section of the website) they used in the last month regardless of whether they visited that module in the site. We assume that some patients will need repeated exposure to skills to gain mastery and incorporate into their routine, whereas other patients may visit a module once and be able to incorporate it into regular practice.

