#### *Control group*

Patients in the control group will undergo an active control intervention in which they receive open access to a separate website (<https://monitoringprogress.org/>) that contains only the Monitoring Progress symptom tracker subpage over the 6-month study period. Control group participation will also be divided into an active (12-week) phase and a maintenance (3-month) phase. Similar to the intervention group, the control group will receive a weekly text or email prompt directing them to track a specific symptom or activity during the active phase of that study. During the maintenance phase of the study, they will receive monthly prompts to the Monitoring Progress subpage (without prompting to a specific symptom or activity).

Control participants will receive a questionnaire battery at 3-month interval (primary endpoint) and 6-month interval (secondary endpoint).

Both patients in the intervention and control groups will receive contact from the study team at the same intervals throughout the study. If questionnaires are not completed within 4 days, an automatic reminder email will be sent. If questionnaires are not completed within 7 days, a study member will call with a reminder. If questionnaire is not completed with 14 days, a study member will call with another reminder. Patient will be considered lost to follow up if they fail to complete the 6-month questionnaire within 21 days after survey invitation. Both intervention and control groups will continue to follow with their specialty gynecologist and will receive usual care throughout the study period. On average, patients follow up every 3-4 months in this clinic per their physician recommendation and we will not recommend any specific changes to usual care follow up as part of this study.

A participant is considered to have completed the study if they have completed the baseline questionnaire and the 3-month questionnaire.

After completion of 3-month questionnaire, we will be performing focus groups for approximately one-half of the patients in the intervention group (n=20) in order to obtain in-depth feedback regarding the program and potential adjunct therapies for future studies. Patients in the intervention group may decline this invitation and still be considered to have completed the study.

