#### 8.4.4 TIME PERIOD AND FREQUENCY FOR EVENT ASSESSMENT AND FOLLOW-UP

The occurrence of an adverse event (AE) or serious adverse event (SAE) may come to the attention of study personnel during study visits and interviews of a study participant presenting for medical care, or upon review by a study monitor.

All AEs, not otherwise precluded per the protocol, will be captured on the appropriate case report form (CRF). Information to be collected includes event description, time of onset, clinician's assessment of severity, relationship to study procedures (assessed only by those with the training and authority to make a diagnosis), and time of resolution/stabilization of the event. All AEs occurring while on study will be documented appropriately regardless of relationship. All AEs will be followed to adequate resolution.

Any medical or psychiatric condition that is present at the time that the participant is screened will be considered as baseline and not reported as an AE. However, if the study participant's condition deteriorates at any time during the study, it will be recorded as an AE.

Changes in the severity of an AE will be documented to allow an assessment of the duration of the event at each level of severity to be performed. Documentation of onset and duration of each episode will be maintained for AEs characterized as intermittent.

Study coordinator will record events with start dates occurring any time after informed consent is obtained until 7 (for non-serious AEs) or 30 days (for SAEs) after the last day of study participation. At each study visit, the investigator will inquire about the occurrence of AE/SAEs since the last visit. We will primarily rely on patient self-report of adverse events and will not proactively search internal or external medical record systems to identify these. Events will be followed for outcome information until resolution or stabilization.

---

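### Adverse events have no planned summary by arm (9.4.4 is N/A), and 8.4.4 ties AE inquiry to study visits that the remote follow-up does not contain

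*Combined protocol and SAP*

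**What the plan says.** - **Analysis.** The section headed "9.4.4 SAFETY ANALYSES" contains only N/A. No other part of section 9 mentions adverse events.
- **Collection.** Section 8.4.1 lists three trial-specific AEs (emergency department evaluation for pain, scheduled gynecologic surgery for pain, a positive suicidal-ideation screen). Section 8.4.2 lists the SAEs. Section 8.4.3 grades severity and relatedness, and 8.4.4 requires events to be documented whatever their cause.
- **Inquiry.** Section 8.4.4: "At each study visit, the investigator will inquire about the occurrence of AE/SAEs since the last visit". The same section adds: "We will primarily rely on patient self-report of adverse events and will not proactively search internal or external medical record systems".
- **Timing.** In section 1.3 the row "Adverse Event Reporting" is marked at every month from 0 to 6 and is not limited to one arm.
- **Intervention arm.** A monthly survey runs at months 1 to 6 (1.3, 5.5). Section 8.2 describes its content: "we will send an email link to a survey once per month which will ask which skills" were used. No AE item is mentioned.
- **Control arm.** Section 8.2: "Control participants will receive a questionnaire battery at 3-month interval (primary endpoint) and 6-month interval (secondary endpoint"). Controls also get a weekly prompt for 12 weeks and then monthly prompts, and 8.2 states that the study team contacts both arms at the same intervals.

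**The concern.** Two parts of the safety plan do not work as written.

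First, events are to be collected, graded and recorded, but nothing says they will be set out by randomised arm. Sections 8.4.5 and 8.4.6 provide for reports to the IRB and NIH. That is case reporting, and it does not show whether events were more frequent in one arm.

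Second, the instruction on when to ask refers to an occasion that follow-up does not include. After the telephone screen and consent call, sections 7.3 and 8.2 describe only emails, texts, online questionnaires and reminder calls. Clinic attendance every 3 to 4 months is usual care, not a study visit. With self-report as the main source and no proactive record search, ascertainment depends largely on patients being asked, and the plan does not say who asks, with what question, or when.

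The protocol itself makes the question relevant. Section 2.3.1 expects that new physical activity can bring temporary increases in myofascial pain, and pain exacerbation is central to the AE and SAE definitions. The pilot is meant to inform a definitive trial, and a usable safety table would be a natural product of it.

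**Working it through.** **1. Scheduled questionnaires and surveys after baseline (1.3, 8.2)**

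| | Months | Count |
|---|---|---|
| Intervention: questionnaires at 3 and 6, survey at 1 to 6 | 1, 2, 3, 4, 5, 6 | 6 of 6 |
| Control: questionnaires at 3 and 6 | 3, 6 | 2 of 6 |
| Months with none in the control arm | 1, 2, 4, 5 | 4 of 6 |

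Cross-check against the payments in 5.5: control 3 × $50 = $150; intervention $150 + 6 × $5 = $180, or $180 + $100 = $280 with a focus group. These reproduce the protocol's totals, so the six monthly surveys do belong to the intervention arm alone.

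**2. Scheduled prompts (5.4, 8.2)**

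Each arm: 12 weekly + 3 monthly = 15. Controls have some scheduled contact in 6 of 6 months.

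**3. What is known about AE inquiry**

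- Months marked for AE reporting: 0 to 6, all participants (1.3).
- Occasion stated for asking: study visits (8.4.4). Follow-up study visits described: none.
- Instrument named: none. The measures listed in section 3 include no AE form, and the monthly survey is described only as asking about skills.
- Defined routes for particular events: the depression screen at baseline, 3 and 6 months in all participants leads to the suicidal-ideation AE (8.3). Data on interim surgery are collected at 6 months (6.5; 2.3.1 adds 3 months).
- Events without a defined prompt: emergency department evaluation and hospitalisation for pain.

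**4. How unequal capture would act (assumed figures, not in the documents)**

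If both arms have the same true risk p, and fractions s_I and s_C of events are captured, the apparent risk ratio is (p × s_I)/(p × s_C) = s_I/s_C. With s_I = 0.90:

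- s_C = 0.90: 0.90/0.90 = 1.00
- s_C = 0.70: 0.90/0.70 = 1.29
- s_C = 0.50: 0.90/0.50 = 1.80

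Lower capture among controls would make the intervention look less safe than it is. The documents give no capture rates, so this shows direction and a range, not an estimate.

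**5. What a descriptive table could show**

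A 2:1 split of 69 is nominally 46:23 (blocks of 4 cannot be divided exactly 2:1, so the realised split may differ). With zero events the upper limit of the exact two-sided 95% interval is 1 − 0.025^(1/n):

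- n = 46: 1 − 0.025^(1/46) = 7.7%
- n = 23: 1 − 0.025^(1/23) = 14.8%

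These limits show what the table would offer. They do not measure the defect.

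Power for a formal test at 46 vs 23, two-sided 5%, under assumed AE risks (normal approximation / Fisher):

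- 10% vs 5%: 8% / 3%
- 20% vs 10%: 16% / 14%
- 30% vs 10%: 45% / 42%
- 40% vs 10%: 77% / 74%

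This supports a table with intervals rather than a test.

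**The case against.** In support of the plan one can say the following.

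- **Contact is equal.** Controls are prompted weekly and then monthly, and 8.2 says both arms are contacted at the same intervals (6.3 says essentially the same). This stands. A reader might infer from the schedule that controls go without contact in four of six months. That is wrong: what they lack in those months is a questionnaire or survey.
- **The count of 6 against 2 is not a count of AE inquiries.** This stands too. The monthly survey is not described as asking about events, and the schedule marks AE reporting in both arms alike. Unequal capture is a plausible risk, not a documented feature.
- **Asking is not the only route.** Section 8.4.4 says self-report is the primary source, not the sole one, and allows for events noticed when a patient presents for care. The depression screen is the same in both arms. The full questionnaires are not reproduced, so an AE item in them cannot be ruled out. All of this limits the concern, but none of it supplies the missing rule on how the monthly reporting is done.
- **This is a pilot.** It has no safety endpoint (section 3) and is not powered even for pain interference (9.2). That is a good reason not to plan a safety test. It is not a reason to omit counts by arm.
- **The table would miss minor flares.** The temporary pain increases foreseen in 2.3.1 mostly fall below the listed AEs, unless recorded as deterioration under 8.4.4. That is correct, and the table should not be presented as settling that question.

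**Conclusion.** The point holds in three parts: no by-arm AE/SAE summary is planned; AE inquiry is tied to follow-up visits that are not described; and no instrument is named for the monthly AE reporting in section 1.3. To these is added a risk of unequal capture, because scheduled questionnaires or surveys fall in 6 of 6 follow-up months in the intervention arm and 2 of 6 in the control arm. The size of that risk is unknown; the ratios of 1.00 to 1.80 above rest wholly on assumed capture rates.

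A reader might go further and conclude that the trial cannot make a fair safety comparison. The documents do not support that. They set no safety hypothesis, mark AE reporting equally in both arms, and do not show that the intervention arm is asked about events more often. The defect is an unworkable instruction and a missing table. It should be corrected, but it does not undermine the trial's primary comparison.

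**What to change.** Reconcile sections 1.3, 8.2, 8.4.4 and 9.4.4 as follows.

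1. In 8.4.4, replace the reference to study visits with one fixed AE question, worded identically and asked at the same times in both arms. At a minimum it goes into the 3- and 6-month questionnaires. If the monthly reporting in 1.3 is kept, ask it monthly in both arms, for example through the prompts already sent; if not, amend the row in 1.3.
2. In 9.4.4, replace N/A with a descriptive table by randomised arm: number and percentage of patients with any AE, with each listed AE and with any SAE, with exact 95% confidence intervals. State that no powered safety comparison is intended.

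Cost: one extra questionnaire item and one table. If monthly inquiry is kept, the question is added to existing messages, with a small added burden on participants and on the staff who follow up the answers.
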